5. Subjects with a history of an eating disorder requiring medical or behavioral treatment within the past 10 years.
6. Subjects with prior small bowel or colonic surgery (excluding appendectomy or cholecystectomy if over 6 months since these 2 procedures)
7. Oral antibiotic use in the past 3 months
8. Any planned significant changes in dietary or exercise regimen within 30 days prior to Screening or during the study.
9. Currently pregnant or breastfeeding.

Concomitant Medications

[figure not shown]
Subjects will be allowed to remain on their current IBS medications, provided a stable dose in the past 30 days and they fulfill entry criteria for symptom frequency and severity.

Study Design

This pilot study is designed to assess the comparative effectiveness of MD with LFD. Approximately 20 subjects will undergo a seven-day baseline screening period during which symptoms will be recorded. If a subject doesn't meet all eligibility criteria in the first seven days of the baseline screening period, the screening period can be extended up to 21 days. Subjects meeting all eligibility criteria will be randomized in a 1:1 ratio to receive either the MD or the LFD for a four-week period.

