All continuous variables will be tested for normality using the Shapiro-Wilk test. Normally distributed continuous data will be presented as mean (+/- SD) and will be compared pre-and post-dietary interventions using paired Student's t-test. Continuous data which are not normally distributed will be presented as median (range) and compared using Wilcoxon signed-rank test. Proportions will be expressed as percentages and compared using a chi-square test or fisher exact test as appropriate. As this is a pilot feasibility study, a sample size of 20 patients will allow us to get data on the outcomes and non-inferiority margin needed to power the larger Phase III multi-centered trial.

Potential difficulties

One of the potential difficulties might be the difficulty in patient recruitment for the study. Our group has successfully completed several pharmacological and diet-based RCTs in this patient population and has been able to recruit a much larger sample size for previous studies. However, to ensure we can recruit the required sample size, we will assign a study coordinator who will dedicate a significant proportion of her/his time to

recruiting patients from our functional and general GI clinics. Online and on-site advertisements will also be utilized to recruit patients from general gastroenterology and primary care clinics. We will further utilize a novel digital recruiting tool called “My GI Health” which will identify potential study subjects through social media platforms. We feel that this study will be attractive as we will be providing meals for the duration of the study. In addition, the lack of a placebo group will ensure that all participants will receive a potentially beneficial diet intervention. Other potential difficulties include patients being non-compliant with the diet. We are providing meals to all participants to minimize this and will obtain a daily food log, 3-day recall as well as MEDAS (Mediterranean Diet Adherence Scale) to ensure that our patients are compliant with their allocated diet arm.

Limitations

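### A loosely specified Shapiro-Wilk gate chooses both the summary and the pre/post test for the exploratory continuous data, and no branch promises the mean and SD of change or a between-diet comparison

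*Combined protocol and SAP*

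**What the plan says.** The rule is in the Statistical Analysis section of the combined protocol and SAP. It opens with "All continuous variables will be tested for normality using the Shapiro-Wilk test". Variables that pass are given as mean and SD and "will be compared pre-and post-dietary interventions using paired Student's t-test". For the rest, "Continuous data which are not normally distributed will be presented as median (range) and compared using Wilcoxon signed-rank test". Proportions go to a chi-square or Fisher test. The section closes by saying that 20 patients will allow the team to "get data on the outcomes and non-inferiority margin needed to power the larger Phase III multi-centered trial".

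Other sections that bear on this:

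- Study Design: "Approximately 20 subjects will undergo a seven-day baseline screening period", and those eligible are "randomized in a 1:1 ratio to receive either the MD or the LFD".
- Endpoints: the primary endpoint and all four secondary endpoints are responder proportions. Seven exploratory endpoints are defined as mean changes: stool frequency, abdominal discomfort, IBS-QoL, anxiety, fatigue, brain fog and sleep quality. Breath hydrogen and methane are also exploratory, and the MEDAS adherence score is collected at start and end.
- Specific aims, Aim 2: the two diets are to be compared on clinical and disease-specific quality-of-life endpoints.

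No section fixes a summary for continuous data independently of the gate.

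**The concern.** A rule that lets the data choose the analysis leaves the analysis open until the data are seen, and this rule is also incomplete. It does not give the quantity tested (raw score or within-patient change), the grouping (by arm or pooled), the significance level, or what happens when one arm or one visit passes and the other fails. The paired t-test relies on the distribution of the differences, which the rule does not mention.

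Three things follow for the continuous data:

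1. The same endpoint could appear as mean and SD in one arm and as median and range in the other.
2. An endpoint defined as a mean change would not be reported as one whenever the non-normal branch applies.
3. The SD of change, which is needed to plan any later trial with a continuous endpoint, is not promised in either branch. Nor is a comparison between diets, because both named tests are pre/post.

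**Working it through.** **The plan's own figure.** The sample size of 20 has no calculation behind it, so there is nothing to reproduce. At 1:1 allocation, 20/2 = 10 per arm. If 20 is the number entering screening, as Study Design can be read, 10 is an upper figure.

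**Assumptions not in the documents.** Gate level 5%; gate run within each arm on raw values; both arms drawn from the same distribution; score distributions as named below. With p the Shapiro-Wilk rejection rate at n = 10, the chance that the arms get different verdicts is 2p(1 - p).

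| Distribution (simulated, except normal) | p at n = 10 | 2p(1 - p) |
|---|---|---|
| Normal | 0.05 | 2 × 0.05 × 0.95 = 9.5% |
| 0-10 score, rounded normal, mean 5, SD 2 | 0.115 | 2 × 0.115 × 0.885 = 20% |
| 0-21 score, rounded gamma, mean 6, SD 5 | 0.31 | 2 × 0.31 × 0.69 = 43% |

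The third row also shows the low power of the gate: it misses clear skew in about 69% of samples of 10.

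**Across the seven mean-change endpoints.** If all are perfectly normal and independent, the chance of at least one mismatch is 1 - 0.905^7 = 50%. With correlations of 0.3 to 0.8 between endpoints, simulation gives 43-49%, so independence matters little.

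**If the change is gated instead.** For the same skewed 0-21 score, with an assumed pre/post correlation of 0.3 to 0.7 and no mean shift, p is 0.11 to 0.15. Disagreement is then 2 × 0.11 × 0.89 = 20% to 2 × 0.15 × 0.85 = 26%.

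**If the gate is run once on the pooled 20.** There is one verdict per variable, so the arms cannot differ. The non-normal branch is still taken often for skewed data: rejection at n = 20 is 53% for a gamma with shape 2, against 24% at n = 10.

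**Does the choice of raw values or change matter?** With a skewed baseline (gamma, shape 2, scaled by 1.5) and normal changes (mean -1, SD 1) at n = 10, at least one raw time point failed while the change passed in 27% of samples. In those cases, if failure at either time point selects the signed-rank test, it is used although the changes met the t-test assumption.

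**Does an SD of the values stand in for the SD of change?** With equal SDs at both visits, SD(change)/SD(value) = √(2(1 - r)). This is 1.26 at r = 0.2, 1.00 at r = 0.5 and 0.63 at r = 0.8 (r assumed). It does not, unless r is reported too.

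**What reporting the SD of change would give.** From the chi-square distribution, the 95% CI is 0.69 to 1.83 times the estimate at n = 10, and 0.76 to 1.48 times when pooled within arms on 18 degrees of freedom. That is imprecise but usable.

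**Power given up by fixing one test in advance.** At n = 10 and a true change of 1 SD, paired t has 80% power and signed-rank 79% for normal changes; for skewed changes (gamma, shape 2) the figures are 93% and 95%. The gate therefore protects very little. These figures are for the within-arm test only.

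**The case against.** The strongest reply is that the reach is small and part of the mechanism is a reading of the text. Most of that stands.

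- **Primary and secondary endpoints.** A reader might infer that the gate undermines the pilot's purpose of informing a larger trial. The documents do not support this. The primary and four secondary endpoints are proportions that the gate never touches, and powering a trial on the responder endpoint needs response rates and a margin, not an SD. The text asks for data on the outcomes, the margin and preliminary efficacy data; it does not name SDs. The team will also hold the patient-level data and can compute an SD whatever the report shows.
- **Wrong quantity tested.** A reader might infer that the plan tests raw values by arm. It states neither. Because the exploratory endpoints are defined as mean changes, the variable can fairly be read as the change, which is the right object for a paired t-test. The documented defect is that the rule is silent.
- **Inconsistent arm comparisons.** No between-arm test of continuous data is planned, so there is none for the gate to disturb. Only the side-by-side summaries could differ.
- **Remedy.** Fixing the summary and test in advance would be enough to cure the gate. Covariance adjustment answers the separate absence of a between-arm analysis and is one reasonable choice among several.

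The objection leaves untouched that the rule is data-driven and incomplete, that its non-normal branch does not report the endpoints as defined, and that the SD of change and the comparison of diets are promised nowhere for continuous data.

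**Conclusion.** The point holds as a minor reporting and specification flaw confined to the exploratory and descriptive continuous data: the seven mean-change endpoints, breath gas and MEDAS. It does not affect the primary analysis, the secondary endpoints or the sample size of 20.

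The conflict between the median (range) branch and the mean-change definitions, and the absence of an SD of change and of a between-diet comparison, rest on the text alone. The mismatch between arms is conditional. It is about 10% to 43% per variable, depending on the distribution, if raw values are gated by arm at 5% with 10 per arm. For the skewed score it is about 20-26% if changes are gated, and it is zero if the gate is run once on all 20. The documents do not say which applies, so none of these figures should be quoted as what the plan will produce.

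**What to change.** Delete the normality gate from the Statistical Analysis section. For every continuous endpoint, state in advance that the report will give:

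1. By arm, the number of patients and the mean and SD of within-patient change, with median and quartiles as added description.
2. The between-arm difference in change, adjusted for the baseline value (ANCOVA), with a 95% CI and labelled exploratory.
3. One named rank-based analysis as a fixed sensitivity analysis, run whatever the distribution looks like.

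Item 1 supplies the mean changes as the Endpoints section defines them and the SD of change. Item 2 supplies the comparison that Aim 2 describes. The cost is a few lines of SAP wording. No patients, visits or measurements are added, because the seven mean-change endpoints already have baseline values planned, from the Day 0 questionnaires or the daily entries in the screening period.

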The Mediterranean diet (MD), a time-honored diet rich in plant-based foods and monounsaturated fat, such as olive oil, but low in saturated fats, dairy, and meat,⁸ has recently been considered a therapeutic dietary strategy for IBS. MD has been shown to have cardiovascular benefits in regard to both incidence and mortality,^{9,10} along with other benefits such as the decreased risk of overall mortality, cognitive disorders, and diabetes.¹¹ It is hypothesized that it could also be beneficial in reducing bowel symptoms due to its positive impact on the gut microbiota^{12,13} and microscopic inflammation,^{14,15} lower intake of saturated fat, and regulation of the gastro-colonic reflex.¹⁶ A population-based, cross-sectional study from Italy found the presence of IBS in the general population to be associated with low adherence to an MD.¹⁷ Furthermore, lower adherence to the MD has been associated with more severe abdominal pain and flatulence in patients with IBS.¹² However, it is not clear whether the lower adherence to MD causes more IBS symptoms or whether patients with IBS are more likely to avoid the MD due to worsening symptoms on this diet. A small, open-label study compared the efficacy of three dietary interventions, LFD, gluten-free diet, and MD, in IBS.¹⁸ Each patient followed the three diets for 4 weeks each. All three diets reduced symptom severity ($p<0.01$), abdominal bloating ($p<0.01$), and abdominal pain ($p<0.01$) when compared to baseline. Interestingly, 86% of patients preferred the Mediterranean diet ($p<0.01$). Limitations of the study include the small sample size, carry-over effects as well as lack of randomization, blinding, or assessment of adherence to the diet interventions. ***Despite this initial supportive evidence, no randomized controlled trial has investigated the efficacy of MD in IBS and MD is not routinely used in managing IBS symptoms.*** Therefore, there is a need to evaluate the efficacy of MD in managing IBS symptoms. ***Our overall objective is to compare the clinical efficacy of the MD with the LFD in patients with IBS in a single-center, parallel-group, randomized controlled trial.***

In this study, **we hypothesize that:**

1. LFD and MD groups will achieve a similar improvement in abdominal pain
2. Both groups will achieve similar improvements in bloating, overall IBS symptom severity, and adequate relief

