We plan to test our hypotheses and thereby, accomplish the objective of this application by pursuing the following 2 specific aims:

Aim 1: Compare the clinical effectiveness of MD vs. LFD by comparing the proportion of weekly responders to abdominal pain for at least 2 of the 4 weeks (measured using a decrease in the weekly average of worst abdominal pain in the past 24 hours score of at least 30% compared with baseline)

Aim 2: Compare the efficacy of MD vs. LFD on pre-specified clinical and disease-specific quality of life endpoints in patients with IBS

A positive result to the study will have a significant impact on the treatment of patients with IBS by expanding the armamentarium of evidence-based dietary interventions to include MD (the current quality of evidence is poor to make any recommendations about MD in IBS). If both the groups have similar clinical efficacy, MD could be less cumbersome, less restrictive, and a healthier dietary option for IBS compared to LFD. However, if the study shows MD is inferior to LFD in patients with IBS, this study will still be pertinent to patients with IBS and clinicians, given the increasing popularity of MD in the US.

Significance

Irritable bowel syndrome (IBS), characterized by abdominal pain in association with altered stool form or frequency, affects up to 10% of the general population worldwide.¹ The condition is a disorder of gut-brain interaction and is chronic with a relapsing and remitting natural history.¹⁹ Costs to health services and society are substantial,^{20,21} and the impact of symptoms on quality of life is considerable, with patients willing to accept a median 2% risk of sudden death with a hypothetical medication in return for a 98% chance of symptom cure.²² However, the efficacy of most drugs is modest, and placebo response rates are high.²³ Even novel, more selectively targeted, therapies developed over the last 20 years produce a therapeutic gain over placebo of only 10%–15% and are expensive.²⁴ As a result, treatment satisfaction remains poor with the majority of both prescription and over-the-counter pharmacological options.²⁵

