- Abdominal Discomfort Intensity: The abdominal discomfort score is a single-question, 11-point numeric rating scale in which 0 represents no abdominal discomfort and 10 represents the worst possible abdominal discomfort. Once per day, subjects will report their worst daily (in the past 24 hours) abdominal discomfort.
- Abdominal Bloating: The abdominal bloating score is a single-question, 11-point numeric rating scale in which 0 represents no abdominal bloating and 10 represents the worst possible abdominal bloating. Once per day, subjects will report their worst daily (in the past 24 hours) abdominal bloating.
- Stool Frequency: Subjects will report the number of bowel movements over the previous 24 hours.
- Stool Form: Subjects will use the Bristol Stool Scale (BSS) to report the form of each bowel movement over the previous 24 hours.
- IBS Medication: Subjects will be asked whether they used an IBS medication over the previous 24 hours that is not typically taken daily (i.e., prn antispasmodic, loperamide or laxative).
- IBS-Adequate Relief: Subjects will provide a binary (yes or no) response to rate the adequacy of relief of global IBS symptoms at the start of the study and weekly thereafter.
- Quality of Life: Subjects will report quality of life measures specific to IBS using a validated 34-point questionnaire at the start and end of the study.
- IBS-SSS: Subjects will complete the IBS Symptom Severity Score questionaries at the start of the study and weekly thereafter
- Non-GI symptoms: non-GI symptoms often associated with IBS including fatigue, "brain fog", and quality of sleep will be assessed at the start and end of the study. Fatigue and brain fog will be scored using an 11-point numeric rating scale. Sleep quality will specifically be assessed with the PROMIS Sleep questionnaire.
- Anxiety: Anxiety will be assessed via GAD-7 score at the start and end of the study.

- Diet compliance: Patients will fill out the Mediterranean Diet Adherence Screener (MEDAS), described below, to assess their adherence to the Mediterranean diet at the start and end of the study. Given there are no high-quality, validated questionnaires to assess LFD adherence, a 3-day diet recall will be obtained at baseline and at the end of the study which will eventually be reviewed by a registered dietitian to confirm adherence to the LFD in the LFD group.

Chart A

	Day 0	Daily	Weekly	Day 28
Abdominal Pain		X		
Abdominal Discomfort		X		
Abdominal Bloating		X		

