- Abdominal pain intensity – Proportion of patients who would be weekly responders to abdominal pain for at least 2 of the 4 weeks. A weekly responder is defined as a decrease in the weekly average of worst abdominal pain in the past 24 hours score of at least 30% compared with baseline.

Secondary Endpoints

- Adequate relief - Proportion of patients who would be weekly responders to adequate relief symptom assessment for at least 2 of the 4 weeks. A weekly responder is defined as adequate relief in symptoms in at least 2 out of 4 weeks of the treatment period.
- IBS-SSS - Proportion of weekly responders for at least 2 of the 4 weeks. A weekly responder is defined as a decrease in the weekly IBS-SSS score of at least 50 points compared with baseline.
- Bloating - Proportion of patients who would be weekly responders to bloating for at least 2 of the 4 weeks. A weekly responder is defined as a decrease in the weekly average of worst bloating in the past 24 hours score of at least 30% compared with baseline.
- Stool consistency: Proportion of patients who would be weekly responders to stool consistency assessment for at least 2 of the 4 weeks. A stool consistency weekly responder will be defined as a 50% or greater reduction in the number of days per week with at least one abnormal stool (defined as BSS 1 or 2 or 6 or 7)

Exploratory endpoints:

- Mean changes in stool frequency, abdominal discomfort, IBS-QoL, anxiety, fatigue, brain fog, and sleep quality will be measured before and after the study.
- Stool and sera will be collected during the study and stored for future analyses. The stool will be stored for microbiome analysis, fermentation indices (short-chain and branched-chain fatty acid profiles), and bile acid profile and serum will be stored for analysis of the effect of diets on permeability using serological markers such as LPS, LBP, Zonulin, and inflammatory cytokines.
- Changes in breath hydrogen and methane pattern with the dietary interventions

Statistical Analysis

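### Aim 2 asks for a Mediterranean versus low-FODMAP comparison on quality of life, but the plan gives IBS-QoL and the other continuous exploratory outcomes only paired pre/post tests

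*Combined protocol and SAP*

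**What the plan says.** - **Specific aims, Aim 2:** "Compare the efficacy of MD vs. LFD on pre-specified clinical and disease-specific quality of life endpoints in patients with IBS".
- **Study Design:** patients are "randomized in a 1:1 ratio to receive either the MD or the LFD", so the arms are independent groups.
- **Clinical Outcome Measures, entry on IBS-QoL:** "Subjects will report quality of life measures specific to IBS using a validated 34-point questionnaire at the start and end of the study".
- **Endpoints, exploratory list:** "Mean changes in stool frequency, abdominal discomfort, IBS-QoL, anxiety, fatigue, brain fog, and sleep quality will be measured before and after the study". Changes in breath hydrogen and methane are a further exploratory item. IBS-QoL has no responder definition and appears in no other endpoint.
- **Statistical Analysis, continuous data:** after a Shapiro-Wilk check, normally distributed data "will be compared pre-and post-dietary interventions using paired Student's t-test". The alternative reads: "Continuous data which are not normally distributed will be presented as median (range) and compared using Wilcoxon signed-rank test".
- **Statistical Analysis, proportions:** "Proportions will be expressed as percentages and compared using a chi-square test or fisher exact test as appropriate".

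The section names no other test. It does not say whether the paired tests are run within each arm or on all patients together.

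**The concern.** Aim 2 needs a contrast between two randomized groups. The tests given for continuous data contrast each patient's end value with the same patient's baseline. Quality of life is the one outcome that Aim 2 names, and it falls entirely under the continuous-data rule.

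Followed as written, the plan produces pre/post p-values for IBS-QoL and no prespecified MD minus LFD estimate. Neither arm is an untreated control, so a pre/post change also contains regression to the mean and placebo response, which the Significance section describes as high in IBS. The Limitations section wants preliminary efficacy data for a larger trial. A between-diet estimate with its interval would serve that purpose, and a pre/post p-value does not.

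**Working it through.** **1. Is there a between-arm route for each outcome?** The documents state no figure to reproduce: 20 is a pilot size given without alpha, power, SD or effect size. The check is to match outcomes to tests.

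| Outcome | Form | Test named | Can compare MD with LFD? |
|---|---|---|---|
| Pain (primary) | Responder proportion | Chi-square or Fisher | Yes |
| Adequate relief, IBS-SSS, bloating, stool consistency (secondary) | Responder proportion | Chi-square or Fisher | Yes |
| IBS-QoL (exploratory; quality of life named in Aim 2) | Mean change | Paired t or signed-rank | No |
| Stool frequency, discomfort, anxiety, fatigue, brain fog, sleep (exploratory) | Mean change | Paired t or signed-rank | No |
| Breath hydrogen and methane (exploratory) | Change in pattern | Paired t or signed-rank, if continuous | No |

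Patients in different arms are not paired. Run per arm, the tests give two separate pre/post results. Run on all patients together, they give one result that ignores the arm. The linear mixed-effects model under Preliminary data belongs to an earlier reintroduction study.

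**2. How precise would the missing contrast be?** Assume 10 per arm (20 randomized 1:1, no loss), or 8 per arm to allow for loss. For an unadjusted difference in mean change, in SDs of the change score:

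half-width = t(0.975, 2n − 2) × √(2/n)

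- n = 10: 2.101 × 0.447 = 0.940
- n = 8: 2.145 × 0.500 = 1.072

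Study Design says approximately 20 subjects enter screening, whereas Statistical Analysis gives a sample size of 20. If 20 is the number screened, the arms are smaller and the interval is wider.

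**3. What does baseline adjustment gain?** Mean 95% half-widths at 10 per arm, in SDs of the raw score, by simulation with normal data and equal SDs at baseline and end:

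| Assumed baseline-to-end correlation | Change score | ANCOVA | Narrower by |
|---|---|---|---|
| 0.3 | 1.095 | 0.912 | 17% |
| 0.5 | 0.928 | 0.830 | 11% |
| 0.7 | 0.718 | 0.685 | 5% |

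At correlation 0.85 the gain is about 0.6%, and at 0.9 it reverses slightly. With 8 per arm it has reversed slightly by 0.85. At correlation 0.5, the ordinary ANCOVA t-interval covered 95% to 97% with normal, exponential and lognormal data at 8 and 10 per arm, so a normality-based choice of method is not needed.

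**4. Illustration only: two separate paired tests.** Suppose the paired t-test is run per arm at two-sided 0.05 and both diets have the same true standardised change d. With per-arm power p from the noncentral t distribution, P(exactly one arm significant) = 2p(1 − p). At n = 10 and d = 0.5, p = 0.293, so 2 × 0.293 × 0.707 = 0.414.

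| d | 0 | 0.2 | 0.3 | 0.5 | 0.7 | 1.0 | 1.2 | 1.5 | 2.0 |
|---|---|---|---|---|---|---|---|---|---|
| 10 per arm | 9.5% | 16% | 23.5% | 41% | 50% | 32% | 15% | 2.5% | 0% |
| 8 per arm | 9.5% | 14% | 20% | 36% | 48% | 44% | 29% | 9% | 0.5% |

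Equal diets can therefore often give one significant and one non-significant arm. This does not measure the gap itself, and it does not apply if the tests are pooled.

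**The case against.** The case for leaving the plan alone is mainly one of weight. The affected outcomes are all exploratory, the trial is declared a non-definitive pilot, and neither stated hypothesis involves them; the second, for instance, is "Both groups will achieve similar improvements in bloating, overall IBS symptom severity, and adequate relief". The endpoint and its test also agree with each other, since the outcomes are defined as before-to-after changes and tested that way. For the non-quality-of-life outcomes the link to Aim 2 is loose: the four secondary endpoints already satisfy its general reference to clinical endpoints. Arm-level means and SDs, if reported, would let a reader derive a difference.

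Most of this stands and limits the point. It does not remove it. The conflict is between Aim 2 and the endpoint-and-test pair, and for quality of life that conflict is explicit. The plan promises neither the by-arm display nor the contrast.

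Two stronger readings are tempting. A reader might infer that Aim 2 as a whole, or the primary comparison, lacks a between-arm test. The documents do not support that, because those endpoints are proportions with a chi-square or Fisher route. A reader might also infer that the team will treat significance in one arm only as evidence of a diet difference. Nothing in the documents proposes that, and they do not even say that the tests are run per arm.

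**Conclusion.** The point holds for IBS-QoL as a mismatch between a stated aim and the stated method: the named tests cannot give the comparison that Aim 2 calls for. The same gap exists for the other continuous exploratory outcomes, including breath gases where analysed as continuous, but without the direct tie to the aim. It should be fixed, and no primary or secondary conclusion depends on it.

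What is lost is a prespecified MD minus LFD estimate, with an unadjusted 95% half-width of roughly 0.94 to 1.07 SD of change at 10 to 8 per arm. That is useful for planning and is not a decisive test. The matching of aims, endpoints and tests needs no assumption. The numerical figures rest on assumed arm sizes, a 95% level, normal data except where stated, and assumed correlations and effects, because the documents supply none of these. The 0% to 50% range for one-arm significance shows only what could mislead a reader if the tests were run per arm.

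**What to change.** Replace the two paired-test sentences in Statistical Analysis; adding text beside them would leave a contradiction. Suggested wording:

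> For IBS-QoL and each other continuous exploratory endpoint, the MD minus LFD difference will be estimated with a 95% CI from an ANCOVA of the end-of-treatment value on diet arm and baseline value. For daily measures, baseline is the screening-week average and end of treatment is the week-4 average. Within-arm pre/post changes will be summarised descriptively by arm.

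Because screening may extend to 21 days, the text should also say which seven days form the screening-week average. A two-sample comparison of change with a 95% CI would close the gap equally well. ANCOVA is preferable only for its narrower interval at low to moderate correlation.

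The cost is wording. IBS-QoL, anxiety and the non-GI symptoms are already collected at start and end in both arms, stool frequency and discomfort are recorded daily, and breath readings are taken each day. No visit, patient or measurement is added.
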